Protocol title:

Feasibility of using daily Humidified Nasal High-flow with Oxygen during Sleep and/or Daytime in Hypercapnic COPD patients following recent (< 12 wks.) hospitalization for AECOPD for 90 days

NCT03221387

Date: 10/06/2017

1) Abstract of the study

Humidified Nasal High-flow with Oxygen (HNHF-O2) therapy has been reported to have acute beneficial effects in patients with hypoxemic respiratory failure. HNHF-O2 may be beneficial in patients with COPD and chronic impairments in gas exchange, both hypoxemia as well as hypercapnia. HNHF-O2 may decrease work of breathing, reduce dyspnea, improve airway humidification, and potentially stabilize or reduce carbon dioxide levels. However, there is limited data showing the chronic effects of HNHF-O2 in patients with hypercapnic respiratory failure, specifically those discharged to home following hospitalization for an acute exacerbation. Data that demonstrates that HNHF-O2 is well tolerated, and stabilizes or improves gas exchange long term in patients with COPD is lacking. Similarly, data that demonstrates that this therapeutic regimen is feasible to provide to patients in the home environment are lacking. This is an open-labeled pilot study of thirty patients to determine the safety and feasibility of using the device in the outpatient management of patients with COPD.

2) Protocol Title

Feasibility of using daily Humidified Nasal High-flow with Oxygen during Sleep and/or Daytime in Hypercapnic COPD patients following recent (< 12 wks.) hospitalization for AECOPD for 90 days

3) IRB Review History

Not applicable

4) Investigator

[name]

5) Objectives

To assess the feasibility of using daily home HNHF-O2 during sleep and/or daytime in hypercapnic COPD patients following recent (< 12 weeks) hospitalization for AECOPD for 90 days.

6) Background

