current use (\leq 4 weeks of study entry) of any PAP-therapy (e.g., CPAP or NPPV); sleep apnea as follows: STOPBang scores \geq 5 or STOPBang score \geq 2 plus BMI $>$ 35 kg/m²; or Berlin questionnaire scores suggesting high likelihood of sleep apnea with increased risk of sleep-related accident (e.g., occupation as a commercial driver or pilot); or excessive daytime sleepiness (i.e., either of High (>15) score on the Epworth Sleepiness Scale or “fall asleep” accident or “near miss” accident in prior 12 months).

c) Local Number of Subjects

Thirty subjects will be accrued locally for this study.

We expect few screen failures.

d) Study-Wide Number of Subjects

If this is a multicenter study, indicate the total number of subjects to be accrued across all sites. – Not applicable.

e) Study Timelines

- Subjects will be followed for 90 days with regular telephone follow-up and clinic visits throughout.
- Subjects will be enrolled over a period of 12 months.
- The investigators will complete the data analysis approximately 18 months after the first subject is enrolled.

f) Study Endpoints

The primary endpoints of this study are the feasibility of oxygen therapy by HNHF-O2 at home over a 90-day period in terms of tolerance and hours of use. Descriptive statistics will be used to characterize the patient population in terms of demographic factors and severity of airflow obstruction. Changes in PaO₂, PaCO₂ and pH across the days will be done by analysis of variance. The effect of baseline PaCO₂ on change in PaCO₂ with HNHF-O2 therapy will be analyzed as an independent effect on change in PaCO₂ levels with HNHF-O2. Changes in respiratory rate, heart rate, blood pressure accessory muscle use will also be assessed by analysis of variance. Patient tolerance and side effects will also be measured across days of use per patient and across days in all patients as group trends. Hours of use per device log and per patient diary will be independently analyzed and compared to one another. The impact on change in exacerbation frequency and severity will be analyzed. Changes in spirometry, 6MWD, GOLD grade and class and BODE scores prior to and after 90 days of HNHF-O2 will be analyzed.

g) Procedures Involved in the Human Research

[figure not shown]
An overview of the study is provided in the figure below.

Outpatient HNHF-O2 Protocol

Version 3.0

10/06/2017

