The primary endpoints of this study are the feasibility of oxygen therapy by HNHF-O2 at home over a 90-day period in terms of tolerance and hours of use. Descriptive statistics will be used to characterize the patient population in terms of demographic factors and severity of airflow obstruction. Changes in PaO₂, PaCO₂ and pH across the days will be done by analysis of variance. The effect of baseline PaCO₂ on change in PaCO₂ with HNHF-O2 therapy will be analyzed as an independent effect on change in PaCO₂ levels with HNHF-O2. Changes in respiratory rate, heart rate, blood pressure accessory muscle use will also be assessed by analysis of variance. Patient tolerance and side effects will also be measured across days of use per patient and across days in all patients as group trends. Hours of use per device log and per patient diary will be independently analyzed and compared to one another. The impact on change in exacerbation frequency and severity will be analyzed. Changes in spirometry, 6MWD, GOLD grade and class and BODE scores prior to and after 90 days of HNHF-O2 will be analyzed.

This is a pilot study in which the primary outcome is to determine the feasibility of using high-flow nasal oxygen in patients with COPD who have been recently discharged from the hospital with a COPD exacerbation. As such it is not an efficacy trial and is powered based on the ability to detect safety issues or unforeseen problems. The sample size has been estimated based on the method described by Viechtbauer, et.al.⁷

The safety issue we have identified is the need to withdraw therapy because HNHF-O2 is not tolerated by the subject.

The formula for this calculation is based on the probability of observing at least one of these events:

$$P(x > 0) = 1 - (1 - \pi)^n \text{ where}$$

x = the number of events that occur across the total number of participants
and

π = the probability that the event will occur.

Solving for n yields:

$$n = \frac{\ln(1 - \gamma)}{\ln(1 - \pi)}$$

Where γ = the confidence threshold.

Using a 95% confidence threshold and 15% probability that an event (need to discontinue due to intolerance) occurs the sample size required is:

Outpatient HNHF-O2 Protocol

Version 3.0

10/06/2017

$$n = \frac{\ln(1-0.95)}{\ln(1-0.1)} = 28.4 \text{ subjects.}$$

The number of subjects has been increased to 36 to accommodate screen failures and dropouts and to provide evaluable data on 30 subjects.

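### Safety is a stated aim, but the only event named for sizing is withdrawal for intolerance, and no planned analysis would flag a patient who tolerates the device while PaCO2 rises

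*Combined protocol and SAP*

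**What the plan says.** The abstract describes a single-arm study of thirty patients intended "to determine the safety and feasibility of using the device in the outpatient management of patients with COPD". Section 5 is narrower and lists feasibility only: "To assess the feasibility of using daily home HNHF-O2 during sleep and/or daytime in hypercapnic COPD patients". Section 10(i) calls the study a pilot whose primary outcome is feasibility, and then says that it "is powered based on the ability to detect safety issues or unforeseen problems". The one event entered in the sample-size formula follows: "The safety issue we have identified is the need to withdraw therapy because HNHF-O2 is not tolerated by the subject".

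The primary endpoints in 10(f), repeated in 10(i), are tolerance and hours of use. No numerical success criterion is given for either. Changes in PaO2, PaCO2 and pH "across the days will be done by analysis of variance", and baseline PaCO2 is examined as a predictor of the change in PaCO2. Side effects, exacerbation frequency and severity, vital signs and accessory muscle use are also analysed.

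Other safety information is gathered outside the analysis text. The telephone calls in 10(g) ask about vital status and adverse events. Section 10(l) provides a monthly review of all adverse events, with particular attention to discontinuation and to intensified oxygen. It does not mention carbon dioxide or pH.

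**The concern.** The title and objective describe the patients as hypercapnic. The abstract says that long-term gas-exchange data on this therapy are lacking and that it may stabilise or lower carbon dioxide. Whether some patients get worse is therefore a question the protocol itself leaves open.

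The plan has no per-patient answer to it. Analysis of variance describes the average change, and the baseline-PaCO2 model describes how that average varies with the starting value. Neither counts the patients whose hypercapnia worsened. A few large rises can be offset by many small falls, leaving an average near zero while the tolerance endpoint records those same patients as tolerating.

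Two gaps add to this. Deaths and adverse events are collected but have no planned table. The sizing sentence refers to safety issues and unforeseen problems without saying how common a problem must be before 30 patients are likely to show it.

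**Working it through.** **1. The plan's own figure.** Section 10(i) uses n = ln(1 − γ) / ln(1 − π), with γ the confidence threshold and π the event probability.

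- γ = 0.95, π = 0.10: ln(0.05)/ln(0.90) = 28.43. This reproduces the stated 28.4.
- γ = 0.95, π = 0.15: ln(0.05)/ln(0.85) = 18.43. This does not, although the text reads "Using a 95% confidence threshold and 15% probability that an event".

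The displayed formula uses 0.1, so the stated size corresponds to a 10% event rate. Section 10(i) raises enrolment to 36 to obtain 30 evaluable subjects; sections 10(a) and 10(c) say thirty.

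**2. What 30 patients can show.** The probability of at least one event is 1 − (1 − π)^30. The documents give no rates for problems other than intolerance, so a range is shown.

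| True rate | Probability of at least one event in 30 |
|---|---|
| 1% | 26% |
| 2% | 45% |
| 5% | 79% |
| 10% | 96% |

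The rate at which this reaches 95% is 1 − 0.05^(1/30) = 9.5%. If all 36 started the device it would be 1 − 0.05^(1/36) = 8.0%. Zero events in 30 leaves an exact two-sided 95% upper limit of 1 − 0.025^(1/30) = 11.6%.

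**3. What a group-level test can miss.** All values here are assumed. A paired test of baseline against Day 90 stands in for the analysis of variance.

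- Three of 30 patients have a true rise of 12 mmHg and 27 a true fall of 1 mmHg. Mean change = (3 × 12 − 27 × 1)/30 = +0.3 mmHg.
- With a within-patient SD of 4 mmHg per gas, the noise on a change has SD 4 × √2 = 5.66 mmHg. In 20,000 simulated trials the test was significant in about 2%. For within-patient SDs from 2 to 6 mmHg the figure runs from 0.3% to 3.5%.
- Without added noise, 2 patients rising by 10 mmHg and 28 falling by 3 mmHg give (20 − 84)/30 = −2.13 mmHg, SD 3.30, t = −3.54, p = 0.001. The group result is a significant improvement although two patients worsened.

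**4. What a per-patient flag can and cannot do.** Take the same noise and, for illustration only, a margin of 1.96 × 5.66 = 11.1 mmHg. A patient with a true rise of 12 mmHg is flagged about 56% of the time. If nobody truly changes, each patient has a 2.5% chance of being flagged, so at least one of 30 is flagged in 1 − 0.975^30 = 53% of trials. A count needs an interval and a caveat: 3 of 30 is 10%, exact 95% interval 2.1% to 26.5%.

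**5. Whether the change can be read.** The sampling conditions disagree within section 10(g).

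| Place in 10(g) | Condition stated |
|---|---|
| Note 2 to the overview figure, and the baseline text | After 5 minutes on supplemental oxygen, to keep saturation above 90% |
| Footnote to the schedule table | Room air after 20 minutes off the device; 2 L oxygen allowed on desaturation |
| Day 90 list, and the study-procedures text | Room air after 20 minutes off the device |

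The schedule also places a gas at Visit 2, the visit at which the device is started, without saying whether it is drawn before or after the start. A baseline-to-Day 90 change could therefore partly reflect the sampling condition.

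**The case against.** Safety is a thin aim here. The title, section 5 and the primary endpoints speak only of feasibility, and 10(i) says that this is not an efficacy trial. The intolerance sentence supplies an input to a formula; it does not say that nothing else is a safety matter. Side effects are analysed per patient and as group trends, exacerbation frequency and severity are analysed, vital status is checked at six calls, and all adverse events are reviewed monthly. Clinically recognised carbon dioxide retention could be reported as an adverse event.

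Most of this stands, and it rules out several stronger readings. A reader might infer that a tolerating patient who retains carbon dioxide counts as a success. The documents define no success criterion, so such a patient is only recorded as tolerating. A reader might infer that intolerance is the plan's whole definition of safety; it is only the event named for sizing. A reader might also infer that a respiratory admission would go unseen. An admission for an exacerbation would be expected to enter the exacerbation analysis, although severity is not defined.

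The illustration is also open to the charge that its values were chosen so that the mean nearly cancels. That is fair: it shows that masking is possible, not that it is likely. A per-patient flag is noisy, as step 4 of the working shows, and with no control arm it cannot be attributed to the device.

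None of this supplies a per-patient summary of PaCO2 or pH, a planned table of deaths and adverse events, or a limit on the sizing claim.

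**Conclusion.** The point holds in a limited form. Safety is an aim in the abstract and the basis of the sample size. The only event named for sizing is withdrawal for intolerance, and blood gases are analysed only at group level. Individual worsening of PaCO2 in a tolerating patient would be flagged by no planned analysis, and deaths and adverse events have no planned tabulation.

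The detection limit, a true rate of about 10% for 95% probability, follows from the plan's own formula with 30 evaluable patients. The masking figures (+0.3 mmHg, about 2% significant) rest wholly on assumed changes and an assumed SD. The documents do not support a conclusion that the trial would declare the device safe; how it will report is not stated. This is an inexpensive improvement to a pilot, and the feasibility endpoints do not depend on it.

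**What to change.** First reconcile the blood-gas sampling conditions within 10(g), and state when the Visit 2 gas is drawn relative to device start. Without this the change in PaCO2 cannot be interpreted.

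Then add to 10(f) and 10(i) a descriptive safety table over all patients who start the device, beside the intolerance count, giving numbers, percentages and exact 95% intervals for:

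- deaths by Day 90;
- respiratory hospital admissions by Day 90;
- patients whose Day 90 PaCO2 or pH has worsened beyond a margin that the investigators fix before data review.

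Tabulate the adverse events already collected. List the individual PaCO2 and pH changes. Show starters without a Day 90 gas as a separate category with the reason, so that they are not counted as unchanged. State that some patients will cross any margin through measurement noise, and that without a control arm a flag cannot be attributed to the device.

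Restate the sizing sentence: 30 evaluable patients give a 95% probability of seeing at least one event only for problems with a true rate of about 10% or more, with 79%, 45% and 26% at rates of 5%, 2% and 1%. Correct the 15% against 0.1 mismatch at the same time.

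The cost is protocol wording, one extra table and the work of settling the blood-gas procedure; no new visit or test is needed. The downside is a more modest safety statement.

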All data will be stored on the REDCap website and on password protected files on password protected computers located on the 7th floor of the Kresge Building. This is an area with access restricted to study personnel.

j) Confidentiality

All data will be stored on the REDCap website. The site is part 11 compliant. All study personnel have been trained in human subjects protections and good clinical practices. Study data will only be accessible to study personnel via password protected websites and computer terminals.

k) Confidentiality

All data will be stored on the REDCap website. The site is part 11 compliant. All study personnel have been trained in human subjects protections and good clinical practices. Study data will only be accessible to study personnel via password protected websites and computer terminals.

l) Provisions to Monitor the Data to Ensure the Safety of subjects

This study utilizes an FDA-approved device for the delivery of warmed humidified gases for a medical indication included in the 510(k) approval letter. As such, and because of the limited enrollment in this trial, there is no need for a data and safety monitoring board. Monitoring of the study will be done by the principal investigator on a routine (monthly) basis in conjunction with the study sponsor and the Director of Research at the Temple Lung Center. All adverse events will be reviewed with particular attention paid to those subjects who discontinued use of the device and those where oxygen therapy needed to be intensified in order to maintain adequate oxygenation.

m) Withdrawal of Subjects

Subjects may discontinue participation in the study at any point and for any reason. This decision will not be held against them in any way. If a subject decides to withdraw, the physician will assess their clinical condition and determine the best course of action for the subject. This may include alternative methods of oxygen administration. Any data that is collected up to the point of subject withdrawal will be retained for analysis.

11) Risks to Subjects

History and physical exam, vital signs. These are all procedures routinely performed as standard of care and are not associated with any adverse effects.

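### The event the trial is sized on, stopping HNHF-O2 for intolerance, is not counted in any planned analysis, and the protocol sets no item for the reason and no rule for attribution

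*Combined protocol and SAP*

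**What the plan says.** Sections 10(f) and 10(i) give the primary endpoint as 90-day home feasibility, judged by tolerance and hours of use. Section 10(i) then names the event that sets the sample size: "The safety issue we have identified is the need to withdraw therapy because HNHF-O2 is not tolerated by the subject". On the criterion it says: "The formula for this calculation is based on the probability of observing at least one of these events".

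The analysis of tolerance is one sentence, the same in both sections: "Patient tolerance and side effects will also be measured across days of use per patient and across days in all patients as group trends".

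On numbers, 10(i) says: "The number of subjects has been increased to 36 to accommodate screen failures and dropouts and to provide evaluable data on 30 subjects". Section 10(c) says: "Thirty subjects will be accrued locally for this study".

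On leaving the trial, 10(m) says: "Subjects may discontinue participation in the study at any point and for any reason". It adds that a physician assesses the subject at withdrawal and that data collected up to then are kept. It does not ask for the reason, and it does not separate stopping the device from leaving the study.

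**The concern.** A trial sized to observe at least one stop for intolerance should report how many such stops occurred, and out of how many patients. The stated analysis does not. A trend over days of use describes patients while they are still using the device. The patient who could not tolerate it contributes few days and then none, so the group trend can look better as intolerant patients drop out of it.

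The sizing event is also defined by its cause. Without a named item for the reason and a rule for attribution, someone has to decide whether a given stop was intolerance, another reason or an ordinary dropout, and nothing in the protocol guides that decision. The trial is open-label with no control group, so the decision would be made with the patient's course known. At stake is the primary tolerance figure, which could move with classification and choice of denominator alone.

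**Working it through.** **1. The plan's own figure.** Inputs from 10(i): γ = 0.95, and π = 0.10 as printed in the formula.

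n = ln(1 − γ)/ln(1 − π) = ln(0.05)/ln(0.90) = 28.43, which reproduces the stated 28.4 (29 whole subjects).

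The sentence that introduces the formula gives π as 15%: "Using a 95% confidence threshold and 15% probability that an event (need to discontinue due to intolerance) occurs the sample size required is". That value gives ln(0.05)/ln(0.85) = 18.43, or 19 subjects. The two values conflict. This is a separate matter, so both are carried below.

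The chance of at least one event is 1 − (1 − π)^n:

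| n | π = 0.10 | π = 0.15 |
|---|---|---|
| 29 | 95.3% | 99.1% |
| 30 | 95.8% | 99.2% |
| 36 | 97.7% | 99.7% |

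**2. From 36 to 30.** The allowance is 6/36 = 16.7%, covering screen failures and dropouts together. This rate is back-calculated, since the document states none. It does not say what makes a subject evaluable, or whether someone who stops the device early still is.

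**3. What the protocol specifies about a stop.**

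| Needed to count the event | Where it could come from | Specified? |
|---|---|---|
| That the device was stopped | Hours of use at clinic visits and meter time (10(g)); compliance at six calls (10(g)); monthly review attentive to device discontinuations (10(l)) | Probably recoverable |
| When it was stopped | Meter time, patient log, spacing of calls and visits (10(g)) | Approximately recoverable |
| Why it was stopped | Side-effect list and adverse events give indirect evidence (10(g)) | No named item |
| Rule for calling it intolerance | – | None |
| Count or proportion with denominator and interval | Sizing formula defines x as events across all participants (10(i)) | Not carried into the analysis text |

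**4. How far the result can move.** Assumption: 36 start the device and 6 stop. The documents give no expected number of stops; 6 is taken because it equals the 36-to-30 allowance. Exact (Clopper-Pearson) 95% limits for x of n are the 0.025 quantile of Beta(x, n − x + 1) and the 0.975 quantile of Beta(x + 1, n − x). For x = 0 the lower limit is 0 and the upper is 1 − 0.025^(1/n).

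| Handling of the same 6 stops | Result | Exact 95% CI |
|---|---|---|
| All classed as intolerance | 6/36 = 16.7% | 6.4 to 32.8% |
| Half classed as intolerance | 3/36 = 8.3% | 1.8 to 22.5% |
| All treated as dropouts and excluded | 0/30 = 0% | 0 to 11.6% |

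If only 30 start, as 10(c) implies, the results are 6/30 = 20.0% (7.7 to 38.6%), 3/30 = 10.0% (2.1 to 26.5%) and 0/24 = 0%, with upper limit 1 − 0.025^(1/24) = 14.2%. In general, k stops among n starters can be reported as anything from 0 to k/n.

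**5. Effect on the chance of seeing an event.** If only a share s of intolerance stops is identified as such, the chance becomes 1 − (1 − πs)^n. The shares are assumptions with no source in the documents.

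| s | π = 0.10, n = 29 | π = 0.15, n = 30 |
|---|---|---|
| 1.0 | 95.3% | 99.2% |
| 0.7 | 87.8% | 96.4% |
| 0.5 | 77.4% | 90.4% |

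**The case against.** The strongest reply is that the protocol says a good deal about stops. Use is metered and logged, calls check compliance and problems, clinic visits go through nine named side effects, and the monthly monitoring pays particular attention to subjects who gave up the device. The sizing formula also names the event and its denominator. This stands. It means the fact and approximate date of a stop are probably available, and the side-effect data give contemporaneous evidence about cause. It does not supply the reason itself, a rule for attribution or a counted result.

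A reader might infer that no form records a stop or its reason. The documents do not support that. The case report forms are not among them, and absence from a schedule is not absence from the forms. Nor does the freedom to withdraw for any reason mean that reasons go unrecorded; that is ordinary voluntary-participation language.

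A reader might also infer that the investigator and sponsor will sort stops after the fact in the monthly review. Section 10(l) describes safety monitoring during the trial, not endpoint classification. The documents do not say who classifies a stop, or when.

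A third tempting reading is that the 95% assurance fails. That depends entirely on unsourced identification shares, and with the 15% rate and 30 subjects it is still 90.4% when half the events are missed.

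Finally, this is a pilot with no tolerance threshold and no go/no-go rule, so no stated decision would reverse. That limits the consequence, but the tolerance figure is still the primary result that a reader will take away.

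**Conclusion.** The point holds in this form: followed as written, the analysis does not deliver the quantity on which the trial was sized. The protocol leaves open why a patient stopped, how a stop is attributed to intolerance, and whether those who stop stay in the denominator.

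In the illustration the same data can be reported as anything from 0% to 16.7%, a range that takes in both the 10% and the 15% used in the sizing section. This rests on two assumptions, 36 starters and 6 stops. Because 36 also allows for screen failures, fewer may start, and the range shifts as shown for 30. The direction of any error is not established. The text permits a favourable figure but does not show that one would be chosen. The change is worth making before analysis because it is cheap and concerns a primary endpoint.

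**What to change.** - **Data (10(g), 10(m)).** At the scheduled calls and clinic visits, record whether the device is still in use and, for any permanent stop, its date and the reason given at the time. Keep stopping the device distinct from leaving the study.
- **Analysis (10(f), 10(i)).** Define discontinuation for intolerance. Make the primary tolerance result the proportion of all who started HNHF-O2 that stopped for intolerance by Day 90, with an exact 95% CI. Report all-cause permanent stops on the same denominator. The trends over days can stay as supporting description.
- **Denominator (10(i)).** Define evaluable so that nobody who started the device is removed for having stopped it.
- **Sensitivity analysis.** Count stops with no documented reason as intolerance. This belongs here rather than in the main result, because in recently hospitalised COPD patients some undocumented stops will reflect illness or loss to follow-up.

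The cost is one recorded item at contacts already planned and a few sentences of analysis text. The sample size and visit schedule do not change. The downside is that the reported tolerance may look less favourable.

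Separately, the 15% and 0.1 event rates in 10(i), and the 30 subjects in 10(c) against the 36 in 10(i), need to be reconciled.

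### The sample-size text assumes a 15% intolerance probability, but the equation uses 10%, so the printed 28.4 subjects does not follow from the stated assumption

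*Combined protocol and SAP*

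**What the plan says.** Section 10(i) of the combined protocol and SAP sizes the pilot by the chance of seeing a problem at least once, not by an efficacy effect. It names one problem: "The safety issue we have identified is the need to withdraw therapy because HNHF-O2 is not tolerated by the subject". It then explains: "The formula for this calculation is based on the probability of observing at least one of these events". The probability is P(x > 0) = 1 − (1 − π)^n, which is solved to n = ln(1 − γ)/ln(1 − π). Here γ is the confidence threshold and "π = the probability that the event will occur".

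The numerical step opens with "Using a 95% confidence threshold and 15% probability that an event (need to discontinue due to intolerance) occurs the sample size required is". The displayed equation that follows is n = ln(1 − 0.95)/ln(1 − 0.1) = 28.4 subjects.

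The section ends: "The number of subjects has been increased to 36 to accommodate screen failures and dropouts and to provide evaluable data on 30 subjects".

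**The concern.** The sentence and the equation that completes it give different values, 15% and 10%, for the same parameter π. Only one of them can produce the printed result.

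This calculation is the only quantitative justification for the size of the study, and tolerance is part of the primary endpoint. A reader cannot tell which intolerance rate the pilot was sized to detect. The two values also give different reasons for the target of 30 evaluable subjects. Under one, 30 is just above the minimum; under the other, it is well above a minimum that the document never prints.

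**Working it through.** **Inputs, all from section 10(i)**

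- Confidence threshold γ = 0.95, the same in the sentence and the equation.
- Event probability π = 0.15 in the sentence and 0.10 in the equation.
- Planned evaluable subjects: 30.

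**Step 1: reproduce the printed figure.** With the equation's inputs, n = ln(0.05)/ln(0.90) = 28.43. This agrees with the printed 28.4, so the displayed arithmetic is right for π = 0.10.

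**Step 2: use the stated assumption.** With π = 0.15, n = ln(0.05)/ln(0.85) = 18.43. This does not agree with 28.4.

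**Step 3: round up to whole subjects and check.** The document leaves the result at 28.4. The whole-number minimum is the smallest n for which 1 − (1 − π)^n reaches 95%.

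| π | Where it appears | n from formula | Minimum whole n | Chance with one fewer | Chance at the minimum | Chance with 30 |
|---|---|---|---|---|---|---|
| 0.10 | equation | 28.43 | 29 | 1 − 0.90^28 = 94.8% | 1 − 0.90^29 = 95.3% | 1 − 0.90^30 = 95.8% |
| 0.15 | sentence | 18.43 | 19 | 1 − 0.85^18 = 94.6% | 1 − 0.85^19 = 95.4% | 1 − 0.85^30 = 99.2% |

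The difference is 29 − 19 = 10 subjects, and 29/19 = 1.53, so the 10% figure is 53% larger. The target of 30 is 30 − 29 = 1 above the minimum at 10%, and 30 − 19 = 11 above it at 15%.

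**Step 4: look for another explanation.**

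- *A digit lost in reading the PDF.* If the equation had contained 0.15 and lost its last digit, the printed result would be 18.4. The result 28.4 confirms that 0.10 was used.
- *A different threshold.* At π = 0.15, a 99% threshold gives ln(0.01)/ln(0.85) = 28.34. That rounds to 28.3, and both the sentence and the equation use 95%.
- *An explanation elsewhere.* No other section gives an intolerance probability or explains a change from 15% to 10%.

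**Step 5: what 30 evaluable subjects can detect.** The smallest π that gives a 95% chance of at least one event is 1 − 0.05^(1/30) = 9.5%, which is below both candidate values.

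**The case against.** The strongest reply is that this is a slip in the prose with no practical effect. The substituted value, the printed 28.4 and the target of 30 all sit comfortably with 10%, and only the sentence says 15%. Thirty evaluable subjects meet the 95% criterion either way. No analysis or monitoring rule in the document uses π, and the study is a small open-label pilot that is expressly not an efficacy trial. On this view the printed number is right and one percentage needs correcting.

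Much of this stands. A slip in the prose is the more plausible reading, and the study is not too small by its own criterion. The printed size is more than required only if 15% was meant; if 10% was meant, the size is right and only the text is wrong. Exceeding the formula's minimum also breaks no rule. At 15% the weakness is only that the calculation no longer explains the choice of 30. Nor does the point need an argument about losses below 30: the target of 30 already allows for dropouts, and a withdrawal for intolerance is itself the event being counted.

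The reply does not remove the contradiction. That 10% was intended is an inference, and the document does not state it. The sentence still claims that a 15% probability requires 28.4 subjects, which is false.

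**Conclusion.** The concern holds. The printed 28.4 (29 subjects) follows from 10%, and the stated 15% requires 18.4 (19 subjects). The document does not settle which was intended. This should be corrected because it is a wrong statement in the study's only sample-size justification. It does not threaten the study: the chance of at least one intolerance withdrawal among 30 evaluable subjects is 95.8% at 10% and 99.2% at 15%.

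That reassurance assumes that 30 subjects are in fact evaluable. Section 10(i) raises the number to 36 to reach 30, whereas section 10(c) says "Thirty subjects will be accrued locally for this study". That conflict is a separate point, but it shows why π should be settled. As an illustration, suppose only 30 were accrued and the plan's own allowance of 6 in 36 were lost from them, leaving 30 × 30/36 = 25. The chance would then be 1 − 0.90^25 = 92.8% at 10%, which misses the criterion, and 1 − 0.85^25 = 98.3% at 15%, which meets it. The assumed loss may be too high, because the allowance includes screen failures, and section 10(c) expects few of those.

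**What to change.** The sponsor should confirm the intended intolerance probability, give its basis, and make the sentence and the equation in section 10(i) agree.

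- **If 10% was intended:** change 15% to 10% in the sentence, keep the equation, and state that 29 subjects are required and that 30 evaluable subjects give a 95.8% chance of at least one event.
- **If 15% was intended:** print ln(0.05)/ln(0.85) = 18.4, state that 19 subjects are required, and give the reason for planning 30 evaluable subjects, with the resulting 99.2%.

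The cost is a short correction to the text or the equation. Neither version adds enrolment, provided 30 subjects are evaluable. The difference between 36 in section 10(i) and thirty in section 10(c) needs its own correction; this one does not resolve it.
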